## Protocol Synopsis:

Title: A Phase II Study of Daratumumab plus Ibrutinib in Patients with Waldenstrom's Macroglobulinemia	
Study Drugs:	Daratumumab and Ibrutinib
Indication:	Waldenstrom's Macroglobulinemia
Study Phase:	Phase II

### Background and Rationale:

While many treatment options are available for Waldenstrom's macroglobulinemia (WM), ibrutinib remains the only approved therapy in both upfront and salvage settings. Data for effective therapies is derived from published Phase 2 studies utilizing rituximab in combination with alkylating agents, purine analogs or proteasome inhibitors with overall response rates (ORR) ~80-95% .

Ibrutinib has demonstrated impressive results as a single agent in previously treated rituximab refractory WM patients with an ORR of 91%, a major response rate of 73%, and a 2 year PFS of 69% . Despite the impressive response rates, the majority of patients only achieve partial responses with the median IgM levels plateauing around 800mg/dL at time of best response. Mutations in genes such as *MYD88*, *CXCR4* and *BTK*, affect response and in the case of *CXCR4* and *BTK*, resistance to ibrutinib . When ibrutinib is held for side effects, surgery or other reasons there is a rapid rise in IgM off of the drug, suggesting ibrutinib is having more of an effect on inhibition of IgM secretion than cell death. These observations provide an opportunity to use novel targeted approaches in combination with ibrutinib to further deepen these response rates in hopes to improve both PFS and OS.

Increasing evidence suggests the cell of origin for WM is an activated memory B cell with ~50-70% of cases demonstrating some level of CD38 expression . Daratumumab is a monoclonal antibody targeting CD38 currently approved for use in multiple myeloma but not approved to treat WM . Using daratumumab in combination with ibrutinib, we seek to target CD38 expression in WM patients both in combination as upfront therapy and as an additive therapy to patients currently on ibrutinib who have reached a response plateau.

### Objectives:

#### Primary Objective:

- To evaluate the safety and toxicity of combination daratumumab and ibrutinib

#### Secondary Objectives:

- To assess overall response rate in Cohort A
- To evaluate the deepening of response in cohort B.
- To evaluate duration of response (DoR)
- To evaluate time to progression (TTP)
- To assess progression free survival (PFS)
- To assess overall survival (OS)

**Exploratory Objectives:**

- Specimens will be collected for future unknown use. Anticipated studies will be determined at a future date. Janssen will retain the right to approve the use of samples for exploratory analysis.

**Methodology:**

We propose a multi-center, two cohort Phase II clinical trial to investigate the effectiveness of adding daratumumab to ibrutinib in WM patients. Cohort A will consist of patients who are ibrutinib naïve and appropriate for ibrutinib based treatment. Cohort B will consist of patients who have achieved a response plateau less than a complete remission (CR) on single agent ibrutinib.

Subjects in Cohort A will be identified by their treating physician and eligible for enrollment if they are treatment naïve or ibrutinib naïve after prior therapy and eligible for ibrutinib based treatment. Subjects in Cohort B will be identified by their treating physician and eligible for enrollment if they have had at least 6 months of exposure to single agent ibrutinib and demonstrate an IgM response plateau defined by two IgM measurements, at least 8 weeks apart that have changed <15% from the previous mark. In Cohort B response assessment will be measured from initial IgM level prior to ibrutinib initiation. Enrolled subjects will be prescribed commercial ibrutinib, 420mg PO daily. The investigational agent, daratumumab will be administered based on FDA approved dosing in multiple myeloma (16mg/kg) with 8 weekly induction treatments during Cycles 1 and 2, followed by every other week dosing for Cycles 3-6, then monthly dosing from Cycle 7 until Cycle 24 at which point they will continue with ibrutinib as monotherapy until Cycle 52 (4 years total) which is the predefined study completion for enrolled subjects at which point they will complete follow-up.

Study visits and response assessments with IgM measurements will occur with each cycle for the first year then every three cycles after cycle 13. Subjects with measurable extramedullary disease will have CT scans every 6 cycles until radiographic CR. Patients will be considered evaluable for response if they completed the initial 8 weeks of daratumumab induction therapy and evaluable for toxicity if receiving one dose of daratumumab. Patients will continue on combination therapy for 2 years or until disease progression or unacceptable toxicities at which point patients will come off trial. Patients achieving a CR after two years of combination therapy will be given an option to continue with single agent commercial ibrutinib.

Subjects to be enrolled	24 total subjects, 12 in Cohort A and 12 in Cohort B
Study Duration	6 years
Accrual period	2 years

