**Inclusion Criteria:**

1. Age  $\geq$ 18 years of age
2. Ibrutinib naïve or previously treated patients currently on ibrutinib with a plateau in disease

response are eligible to participate:

- a. Ibrutinib naïve subjects may be either treatment naïve or previously treated but ibrutinib naïve to enter cohort A.
- b. Subjects entering cohort B must have a plateau response on ibrutinib defined as  $\geq 6$  months of ibrutinib treatment with 2 IgM measurements at least 2 months apart with  $\leq 15\%$  change from the previous measurement. Subjects with IgM level  $< 0.7$  g/dL will be eligible if their IgM level increases  $< 0.15$  g/dL over two subsequent IgM measurements as defined above.
3. Subjects must have measurable disease defined by a serum IgM level  $\geq 0.5$  g/dL
4. Eastern Cooperative Oncology Group performance status of 0-2
5. Hematology values must be within the following limits:
  - a. Absolute neutrophil count (ANC)  $\geq 1000$  mm^3 independent of growth factor support for 7 days prior to study entry.
  - b. Platelets  $\geq 50,000/\text{mm}^3$  independent of transfusion support within 7 days of study entry. TPO mimetics are not allowed to meet criteria.
  - c. Hemoglobin  $\geq 8$  g/dL, independent of transfusion support within 7 days of study entry
6. Biochemical values within the following limits:
  - a. Alanine aminotransferase (ALT) and aspartate aminotransferase (AST)  $\leq 3 \times$  upper limit of normal (ULN)
  - b. Total bilirubin  $\leq 2 \times$  ULN unless bilirubin rise is due to Gilbert's syndrome or of non-hepatic origin
  - c. Creatinine clearance (CLcr)  $\geq 25$  ml/min
7. Women of childbearing potential and men who are sexually active must be practicing a highly effective method of birth control during and after the study consistent with local regulations regarding the use of birth control methods for subjects participating in clinical trials. Men must agree to not donate sperm during and after the study. For females, these restrictions apply for 1 month after the last dose of study drug. For males, these restrictions apply for 3 months after the last dose of study drug.
8. Women of childbearing potential must have a negative serum (beta-human chorionic gonadotropin [ $\beta$ -hCG]) or urine pregnancy test at Screening. Women who are pregnant or breastfeeding are ineligible for this study.

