## 1. Study Objectives

Ibrutinib is an effective treatment strategy for Waldenström's macroglobulinemia (WM) achieving major response rates of approximately 70% in rituximab refractory patients. Unfortunately these responses are generally partial responses (PR) and rapid elevations of IgM occur when the drug is held. This suggests an inability of ibrutinib to address the source of the disease. It is not yet clear whether long-term health risks of persistently elevated IgMs exist and thus we hypothesize we can deepen response rates and increase durability by adding daratumumab to ibrutinib in both treatment naïve and previously treated WM patients who have achieved a disease response plateau on ibrutinib.

We propose a multi-center, two cohort, Phase II clinical trial to investigate the effectiveness of adding daratumumab to ibrutinib in WM patients. Subjects in Cohort A will be identified by their treating physician and eligible for enrollment if they are treatment naïve or relapsed after 1 prior therapy but remain naïve to ibrutinib or BTK inhibitors and appropriate for ibrutinib based treatment. Subjects in Cohort B will be identified by their treating physician and eligible for enrollment if they have had at least 6 months of exposure to single agent ibrutinib and demonstrate an IgM response plateau defined by two IgM measurements, at least 8 weeks apart that have changed <15% from the previous mark. Enrolled subjects will be prescribed commercial ibrutinib, 420mg PO daily. The investigational agent, daratumumab will be administered based on FDA approved dosing in multiple myeloma (16mg/kg) with 8 weekly induction treatments, followed by every other week dosing for cycles 3-6, then monthly dosing, cycle 7-24. Cycle 25 and beyond subjects will continue on single agent ibrutinib. Patients will be premedicated with 100mg of methylprednisolone, 650mg of acetaminophen and 25-50mg IV of diphenhydramine 30 minutes prior to all infusions of daratumumab. Methylprednisolone dosing may be reduced to 60mg with subsequent doses after the first infusion. Subjects will be asked to take 20mg of methylprednisolone for two days after each infusion which can be eliminated after the first cycle at the discretion of the investigator.

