Study visits and response assessments with IgM measurements will occur day 1 of each cycle through cycle 13 then day of 1 every three cycles after the first year on treatment. Subjects with measurable extramedullary disease will have CT scans every 6 months while on study or until radiographic CR at which point they will occur at the discretion of the investigator. Patients will be considered evaluable for response if they completed the initial 8 weeks of daratumumab induction therapy. Response assessment in Cohort B will be measured from the IgM level recorded prior to ibrutinib initiation. Subjects will continue on combination therapy for 2 years until disease progression or unacceptable toxicities at which point patients will stop daratumumab therapy and come off study. All subjects will be followed for 1 year after completing combination therapy unless they come off study early for other reasons. Subjects achieving a CR will be given an option to continue with single agent commercial ibrutinib or stop all therapy.

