### **1.2. Secondary Objectives**

- To assess major response rate with combination daratumumab and ibrutinib cohort A
- To evaluate deepening response rates in Cohort B after daratumumab addition
- To evaluate duration of response (DoR)
- To evaluate time to progression (TTP)
- To assess progression free survival (PFS)
- To assess overall survival (OS)

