#### **7.2. Inclusion Criteria**

- 1)** Subjects must have a diagnosis of WM and meet the requirements for active therapy as defined by the 2nd International Workshop on Waldenstrom's Macroglobulinemia (see **Appendix A** for indications for therapy).
- 2)** Age  $\geq 18$  years of age
- 3)** Ibrutinib naïve or previously treated patients currently on ibrutinib with a plateau in disease response are eligible to participate.
  - a)** Ibrutinib naïve subjects may be either treatment naïve or previously treated but ibrutinib naïve to enter cohort A.
  - b)** Subjects entering cohort B must have a plateau response on ibrutinib defined as  $\geq 6$  months of ibrutinib treatment with 2 IgM measurements at least 2 months apart with  $\leq 15\%$  change from the previous measurement. Subjects with IgM level  $< 0.7$  g/dL will be eligible if their IgM level increases  $< 0.15$  g/dL over two IgM measurements as defined above.
- 4)** Subjects must have measurable disease defined by a serum IgM level  $\geq 0.5$  g/dL
- 5)** Eastern Cooperative Oncology Group performance status of 0-2
- 6)** Hematology values must be within the following limits:

- a. Absolute neutrophil count (ANC)  $\geq 1000/\text{mm}^3$  independent of growth factor support for 7 days of study entry if cytopenias are due to marrow involvement.
- b. Platelets  $\geq 50,000/\text{mm}^3$  independent of transfusion support within 7 days of study entry. TPO mimetics are not allowed to meet eligibility criteria.
- c. Hemoglobin  $\geq 8\text{g/dL}$ , independent of transfusion support within 7 days of study entry

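### The Cohort B plateau rule does not exclude a still-falling IgM, so part of the deepening reported after daratumumab may be continuing ibrutinib response

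*Combined protocol and SAP*

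**What the plan says.** **Entry.** The Synopsis (Methodology) asks for "at least 6 months of exposure to single agent ibrutinib" and two IgM values "that have changed <15% from the previous mark". Section 1 repeats this: "plateau defined by two IgM measurements, at least 8 weeks apart that have changed <15% from the previous mark". The Synopsis inclusion criteria and Section 7.2, criterion 3b, ask for "2 IgM measurements at least 2 months apart" with a change of 15% or less. None of these versions states a direction, a slope or a limit on total change. For IgM below 0.7 g/dL a separate clause applies: such patients "will be eligible if their IgM level increases" by less than 0.15 g/dL. It caps a rise only.

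**Reference value.** Section 1 states: "Response assessment in Cohort B will be measured from the IgM level recorded prior to ibrutinib initiation". The Synopsis says the same.

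**Treatment.** Ibrutinib is taken daily throughout. Section 9.3 gives the one-cycle ibrutinib lead-in to Cohort A only; Cohort B starts directly with Cycle 1 of the combination.

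**Endpoint.** Section 1.2 lists the objective "To evaluate deepening response rates in Cohort B after daratumumab addition". Section 16 names the share of Cohort B patients whose response deepens as a secondary endpoint and keeps the analysis descriptive, with no comparison between cohorts. Neither Section 14 nor Section 16 defines deepening.

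**The concern.** Cohort B is meant to show what daratumumab adds once ibrutinib has done what it can. That reading needs IgM to be roughly flat at entry. Under the stated rule, a patient losing 14% in 8 weeks counts as having reached a plateau. If that fall continues on ibrutinib, it can carry the patient over a category line during combination treatment, and the change will be reported as deepening after daratumumab was added. Because the category is measured from pre-ibrutinib IgM, most of the distance to the line may already have been covered before daratumumab, and only the last small step has to occur on study. With no comparator and no on-study run-in for Cohort B, nothing in the planned output would let a reader see that this had happened. In a cohort of 12, each such patient moves the deepening rate by 1/12 = 8.3 percentage points.

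**Working it through.** **The plan's own figure.** The documents give no figure for deepening. The only design figure is the exact 95% interval for toxicity in Section 16. With 12 × 0.15 = 1.8 events in 12 patients, Clopper-Pearson gives 1.57% to 46.54%, width 44.97%, so it reproduces. It does not bear on this point.

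**Inputs from the documents.**
- Largest admissible change between qualifying values: 15% (Section 7.2), over a minimum gap of 8 weeks (Synopsis, Section 1).
- PR line: IgM at 50% of baseline. VGPR line: IgM at 10% of baseline (Section 14.1, Appendix C).
- Median IgM on ibrutinib alone: 3520 to 880 mg/dL at best response (Section 6.1.5), so 880/3520 = 25% of baseline, a PR.
- Combination treatment: 2 years.

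**Assumptions.** IgM falls by a constant proportion d per 8 weeks on ibrutinib, and daratumumab has no effect. The documents give no value for d after 6 months of ibrutinib, so d is shown at 15%, 10% and 5%. The second worked patient, at 40% reduction (a minor response, IgM at 60% of baseline), is also an assumption. Only the IgM percentage criterion is used; Appendix C adds extramedullary conditions, and Section 14.1 also allows VGPR by IgM normalization.

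**Formulas.** Cumulative fall after w weeks = 1 − (1 − d)^(w/8). Weeks to reach a line = 8 × ln(target/start) / ln(1 − d).

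| Quantity | d = 15% | d = 10% | d = 5% |
|---|---|---|---|
| Fall after 16 weeks | 27.8% | 19.0% | 9.8% |
| Fall after 24 weeks | 38.6% | 27.1% | 14.3% |
| Weeks from 60% to 50% of baseline (MR to PR) | 9.0 | 13.8 | 28.4 |
| Weeks from 25% to 10% of baseline (PR to VGPR) | 45.1 | 69.6 | 142.9 |

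Example: 8 × ln(0.50/0.60) / ln(0.85) = 8 × 0.1823/0.1625 = 9.0 weeks.

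All of the crossings fall within 2 years of combination treatment except PR to VGPR at 5%. Using 14% instead of 15%, to respect the strict inequality in the Synopsis, moves the VGPR time only from 45 to 49 weeks.

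**Does another reading of the rule close the gap?** If the rule is taken as two successive comparisons over three values, a steady fall still passes, because each value is compared only with the one before it. A longer gap does flatten the steepest admissible slope: 15% over 26 weeks is 1 − 0.85^(8/26) = 4.9% per 8 weeks. But the rule sets only a minimum gap. In the low-IgM clause, if it replaces the 15% limit, a fall from 0.7 to the 0.5 g/dL eligibility floor (1 − 0.5/0.7 = 28.6%) is not blocked.

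**The case against.** The strongest reply is that a sustained fall near the limit is a worst case of unknown frequency. Six months of ibrutinib is required first, and the protocol's background describes IgM levelling off at about 800 mg/dL. Carried for a year from the median, the limiting slope gives 880 × 0.85^(52/8) ≈ 306 mg/dL on ibrutinib alone, which is not the plateau described. The patient at 40% reduction also sits near the PR line. In the ibrutinib study in Section 6.1.5, overall minus major response is 90.5% − 73% = 17.5%, or about 2 of 12 if that population applies. The typical patient faces the slower PR-to-VGPR crossing. All of this stands, and it is why the times above are illustrations.

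A reader might infer that the rule biases the deepening rate in favour of the combination. The documents do not support that. A rule blind to direction also admits patients whose IgM is rising by up to 15%, and the low-IgM clause expressly admits a small rise. Those patients work against deepening, and the mix is unknown.

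A reader might also infer that deepening should count only when IgM falls below the value projected from the patient's own pre-entry slope. Two points are too few for that. If a truly flat patient shows −10% by chance, the projection demands 1 − 0.90^(52/8) ≈ 50% by week 52; at −15% it demands 65%. Genuine responders would be disqualified.

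Finally, deepening is undefined, so counting a category change from the pre-ibrutinib reference is the natural reading of the plan but still a reading. The endpoint is secondary and descriptive in a self-described pilot, and the primary safety endpoint is untouched. That lowers the stakes. It does not remove the problem, because the rate will still be read as what followed the addition of daratumumab.

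**Conclusion.** The point holds in a limited form. The plateau rule restricts neither direction nor cumulative drift, and nothing else in the documents closes the gap. Any residual ibrutinib decline that crosses a category line would be credited to daratumumab, at 8.3 points per patient. How soon a line is crossed depends on the slope and the starting level: 9 to 28 weeks from 40% reduction to PR, and 45 to 143 weeks from the documented median to VGPR, for falls of 15% down to 5% per 8 weeks.

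This rests on an assumed constant slope and on deepening meaning a category change measured from pre-ibrutinib IgM. The frequency of such patients and the net direction of bias cannot be stated from the documents. The weakness is in interpreting one secondary endpoint, and reporting can largely deal with it.

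**What to change.** Leave the entry criteria unchanged, apart from reconciling the two wordings of the 15% limit. Keep the response category relative to pre-ibrutinib IgM, and add the following for the deepening endpoint in Section 16:

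1. Report percent change in IgM from Cycle 1 Day 1, and best category change from the category held on that day. Cycle 1 Day 1 IgM is already scheduled (Table 1, Section 9.3.1).
2. Record the qualifying plateau IgM values and their dates in the CRF. They are already needed to establish eligibility.
3. List, patient by patient, the pre-entry IgM change beside the change after daratumumab.
4. Show the deepening rate separately for patients whose IgM was falling before entry and those whose IgM was flat or rising, with the dividing line fixed before the data are examined.

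Do not add a rule that projects the pre-entry slope forward. Changing the reference day does not by itself remove continuing drift; items 3 and 4 are what make it visible.

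The cost is a few CRF fields and one extra table. With 12 patients in the cohort, the two groups in item 4 will be very small and can only be described.

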**Inclusion Criteria:**

1. Age  $\geq$ 18 years of age
2. Ibrutinib naïve or previously treated patients currently on ibrutinib with a plateau in disease

response are eligible to participate:

- a. Ibrutinib naïve subjects may be either treatment naïve or previously treated but ibrutinib naïve to enter cohort A.
- b. Subjects entering cohort B must have a plateau response on ibrutinib defined as  $\geq 6$  months of ibrutinib treatment with 2 IgM measurements at least 2 months apart with  $\leq 15\%$  change from the previous measurement. Subjects with IgM level  $< 0.7$  g/dL will be eligible if their IgM level increases  $< 0.15$  g/dL over two subsequent IgM measurements as defined above.
3. Subjects must have measurable disease defined by a serum IgM level  $\geq 0.5$  g/dL
4. Eastern Cooperative Oncology Group performance status of 0-2
5. Hematology values must be within the following limits:
  - a. Absolute neutrophil count (ANC)  $\geq 1000$  mm^3 independent of growth factor support for 7 days prior to study entry.
  - b. Platelets  $\geq 50,000/\text{mm}^3$  independent of transfusion support within 7 days of study entry. TPO mimetics are not allowed to meet criteria.
  - c. Hemoglobin  $\geq 8$  g/dL, independent of transfusion support within 7 days of study entry
6. Biochemical values within the following limits:
  - a. Alanine aminotransferase (ALT) and aspartate aminotransferase (AST)  $\leq 3 \times$  upper limit of normal (ULN)
  - b. Total bilirubin  $\leq 2 \times$  ULN unless bilirubin rise is due to Gilbert's syndrome or of non-hepatic origin
  - c. Creatinine clearance (CLcr)  $\geq 25$  ml/min
7. Women of childbearing potential and men who are sexually active must be practicing a highly effective method of birth control during and after the study consistent with local regulations regarding the use of birth control methods for subjects participating in clinical trials. Men must agree to not donate sperm during and after the study. For females, these restrictions apply for 1 month after the last dose of study drug. For males, these restrictions apply for 3 months after the last dose of study drug.
8. Women of childbearing potential must have a negative serum (beta-human chorionic gonadotropin [ $\beta$ -hCG]) or urine pregnancy test at Screening. Women who are pregnant or breastfeeding are ineligible for this study.
9. Subjects must sign (or their legally-acceptable representatives must sign) an informed consent indicating that they understand the rational of the study and can participate in all study

procedures.

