#### **Treatment Administration:**

Treatment will be administered on an outpatient basis.

Ibrutinib will be administered as a single dose 420mg tablet daily for a total daily dose of 420mg. Ibrutinib naïve subjects, will have a one month lead-in Cycle -1, with ibrutinib monotherapy prior to initiating combination induction. Subjects in Cohort A who experience any Grade 3 or greater toxicity must have that toxicity resolve to Grade 1 or less prior to daratumumab combination therapy. Subjects will be asked to take a single tablet of ibrutinib orally with or without food. Subjects will take the tab on a continuous daily basis with one cycle of treatment consisting of 28 days. Subjects enrolled on the ibrutinib naïve Cohort A, will take their first dose of ibrutinib before or after their daratumumab infusion. On days in which they do not receive a daratumumab infusion they will be asked to take their ibrutinib tablet at the same time each day. Subjects will continue daily dosing of ibrutinib until disease progression, toxicities, or study completion whichever comes first.

Daratumumab will be administered per the current package insert. Subjects will receive 16mg/kg weekly for 8 total doses during induction. They will then receive 16mg/kg of daratumumab on day 1 and day 15 starting on cycle 3 through cycle 6. Starting with Cycle 7 through cycle 24 subjects will receive daratumumab 16mg/kg on day 1 until disease progression, toxicities or study completion whichever comes first.

Subjects will be premedicated with 100mg of methylprednisolone intravenously (IV), 650mg of acetaminophen PO, and 25-50mg of diphenhydramine IV all given 30 minutes prior to infusions with daratumumab. Methylprednisolone dosing may be reduced to 60mg IV with subsequent doses after the first infusion if no adverse events are recorded. Subjects will be asked to take 20mg of methylprednisolone PO for two days after each infusion and this can be eliminated at the discretion of the investigator after completion of the first cycle.

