#### **6.1.6. Clinical Pharmacokinetics and Metabolism-Ibrutinib**

The absolute bioavailability of ibrutinib administered in capsule formulation after 560mg oral dose was found to be 2.9%. Ibrutinib absorption from the GI tract is complete as there is minimal fecal excretion of unchanged ibrutinib in combination with high levels of oxidative metabolites. Plasma protein binding of ibrutinib in human plasma is 97.3% and 91.0% respectively with a volume of distribution of 683L after an IV dose of 100ug of ibrutinib.

The drug is extensively metabolized by CYP3A mediated metabolic pathways mainly epoxidation of the acryloyl moiety and hydrolysis to form the dihydrodiol. Excretion is predominantly via the feces with approximately 80% recovered mostly within 2 days with only 8% excreted in the urine. The half-life of ibrutinib is 4 to 6 hours.

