#### **6.2.6. Clinical Pharmacokinetics and Metabolism-Daratumumab**

The half-life of daratumumab is both concentration and time dependent. After the first dose of 16mg/kg of daratumumab the half-life was 9 days and is expected to be 18 days with repeated dosing. Exposure efficacy analyses on the data from combination therapies suggest that maximum clinical benefit on progression free survival, duration of response and overall response rate has been attained for the majority of the subjects with an acceptable safety profile at the recommended dose, 16mg/kg. Despite decreasing concentration of daratumumab over time the

current dosing schedule was adequate to produce the concentration level that can maintain the level of target saturation at Q4W dosing interval. Daratumumab peak and trough concentrations at similar timepoints across monotherapy and combination studies have had no impact on the concentration of daratumumab.

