#### **12.2.1. Infusion-Related Events of Grade 1 or Grade 2**

If the investigator assesses an adverse event to be related to the daratumumab infusion, then the infusion should be paused. When the subject's condition is stable, the infusion may be restarted at the investigator's discretion. Upon restart, the infusion rate should be half of that used before the interruption. Subsequently, the infusion rate may be increased at the investigator's discretion.

If the subject experiences a Grade 2 or higher event of laryngeal edema or a Grade 2 or higher event of bronchospasm that does not respond to systemic therapy and does not resolve within 6 hours from the onset, then the subject must be withdrawn from treatment.

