### **12.3. Ibrutinib Administration**

Ibrutinib 420 mg (1m 420mg tablet) is administered orally once daily. The tablet is to be taken around the same time each day with 8 ounces (approximately 240 mL) of water. The tablet

should be swallowed intact and subjects should not attempt to open capsules or dissolve them in water. During treatment days with daratumumab combination dosing, ibrutinib should be taken 0-2 hours prior to daratumumab with 8 ounces of water.

If a dose is not taken at the scheduled time, it can be taken as soon as possible on the same day with a return to the normal schedule the following day. The subject should not take extra capsules to make up the missed dose. The first dose will be delivered in the clinic on Day 1, after which subsequent dosing is typically on an outpatient basis. Ibrutinib will be dispensed to subjects in bottles at each visit. Unused ibrutinib dispensed during previous visits must be returned to the site and drug accountability records updated at each visit. Returned capsules must not be dispensed to anyone.

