## Section 5.3.

If the investigator feels the toxicities outlined above, are likely attributed to ibrutinib dosing, daratumumab dosing may continue without being held after discussion with the study monitor. Upon recovery of  $\leq$  Grade 2, ibrutinib dosing should be the initial drug restarted. Daratumumab infusions should restart at least 7 days after ibrutinib dosing has resumed and there has been no recurrence of the toxicity.

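### Female contraception ends 1 month after an unnamed 'study drug'; if that month runs from the last daratumumab infusion after repeated dosing, about 30-34% of the drug may remain

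*Combined protocol and SAP*

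**What the plan says.** Synopsis inclusion criterion 7 and Section 7.2 criterion 8 require contraception during and after the study, and then set the end point for women: "For females, these restrictions apply for 1 month after the last dose of study drug". For men the period is 3 months. Neither list says which drug starts the clock.

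The term is not used consistently elsewhere. The synopsis header lists both daratumumab and ibrutinib as study drugs. The singular means ibrutinib in Section 12.3.1 (overdose) and daratumumab in Section 13.2 (supply). The synopsis safety assessment, by contrast, counts its 30-day adverse event window from the last dose of either drug.

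The two drugs clear at very different rates. Section 6.1.6: "The half-life of ibrutinib is 4 to 6 hours". For daratumumab after the first 16 mg/kg dose, Section 6.2.6 says that "the half-life was 9 days and is expected to be 18 days with repeated dosing". The same section says that the schedule is adequate to "maintain the level of target saturation at Q4W dosing interval".

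**The concern.** A single month measured from an unnamed drug suits ibrutinib but not necessarily daratumumab. Cover for daratumumab depends on two things that the criterion leaves open: which drug is meant, and how long ibrutinib continues after the last infusion.

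The month can run from an infusion day in two ways.

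- A site reads 'study drug' as daratumumab, the agent that Section 13.2 calls investigational, while ibrutinib is commercial supply.
- Both drugs stop at an infusion. Section 12.2.1 says of certain laryngeal edema or bronchospasm events that "then the subject must be withdrawn from treatment", and Section 12.3 says that on infusion days "ibrutinib should be taken 0-2 hours prior to daratumumab with 8 ounces of water". Under Section 12.4, when a toxicity is attributed to ibrutinib, "daratumumab dosing may continue without being held after discussion with the study monitor", so the last dose of any drug could be an infusion.

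In those cases a woman who follows the rule exactly could conceive with daratumumab near its pre-dose level on monthly treatment. Safety is the trial's primary objective, and this rule protects participants. The other provisions do not close the gap. The only scheduled pregnancy test is at screening (Table 1), and Section 18.1 acts only once a pregnancy has occurred.

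**Working it through.** The plan states no residual-drug figure, so there is none to reproduce. The check uses first-order decay:

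fraction remaining = 0.5^(t / half-life)

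**Inputs**

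- Female contraception period: 1 month, taken as 28 to 31 days because the documents do not define it in days.
- Daratumumab half-life: 9 days after the first dose, 18 days expected on repeated dosing (Section 6.2.6).
- Ibrutinib half-life: 4 to 6 hours (Section 6.1.6).
- Infusion intervals: 7 days in Cycles 1-2, 14 days in Cycles 3-6, 28 days in Cycles 7-24.
- Ibrutinib is taken daily: "Subjects will continue daily dosing of ibrutinib until disease progression, toxicities, or study completion whichever comes first".

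**Half-lives covered by one month**

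- Daratumumab, repeated dosing: 28/18 = 1.6 to 31/18 = 1.7.
- Ibrutinib, at the longer half-life: 28 × 24 / 6 = 112.

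**Month counted from the last infusion**

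- 18-day half-life: 0.5^(28/18) = 34.0%; 0.5^(30/18) = 31.5%; 0.5^(31/18) = 30.3%.
- 9-day half-life (first dose only): 0.5^(28/9) = 11.6%; 0.5^(30/9) = 9.9%; 0.5^(31/9) = 9.2%.

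**Month counted from the last dose of either drug**

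Let L be the number of days that ibrutinib continues after the last infusion, from 0 up to when the next infusion would be due. With a 30-day month, t = 30 + L.

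| Phase | L (days) | Half-life used | Remaining |
|---|---|---|---|
| Induction, after first dose | 0 to 7 | 9 days | 0.5^(30/9) = 9.9% to 0.5^(37/9) = 5.8% |
| Induction, later doses | 0 to 7 | 18 days | 31.5% to 0.5^(37/18) = 24.1% |
| Cycles 3-6 | 0 to 14 | 18 days | 31.5% to 0.5^(44/18) = 18.4% |
| Maintenance | 0 to 28 | 18 days | 31.5% to 0.5^(58/18) = 10.7% |

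Induction as a whole therefore spans about 6-32%, because the half-life lengthens over this phase.

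For women who continue ibrutinib to Cycle 37, the gap from Cycle 24 Day 1 is 13 × 28 = 364 days. Adding 30 days gives 0.5^(394/18) = 0.00003%, which is negligible.

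**Three months after the last infusion**

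90/18 = 5 half-lives. 0.5^(90/18) = 3.1%; 0.5^(92/18) = 2.9%.

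**The case against.** The strongest reply is that no defect in protection is demonstrated. The documents give no fetal-exposure data for daratumumab and no residual level that counts as safe, and target saturation is a measure of drug effect and not of pregnancy risk. This stands. A reader might infer that the plan exposes a fetus to a harmful level, or contradicts itself; the documents support neither.

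A second reply is that 30-34% is an extreme. This also largely stands. A reader might take it as the typical residual, but it needs repeated dosing and a month that starts on an infusion day. The routes to that are narrow. Section 12.2.1 does not say whether withdrawal from treatment includes ibrutinib, and for Grade 4 or life-threatening reactions Sections 12.2 and 12.2.2 stop daratumumab only. Infusion reactions in the primate studies occurred at the first infusion (Section 6.2.4), where the 9-day half-life applies. After a hold under Section 12.4, ibrutinib is the first drug restarted.

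Third, the criterion also requires contraception during the study, and Section 11.1 provides a year of follow-up after combination treatment. A woman in complete response who stops all therapy after Cycle 24, as Section 1 allows, may still be covered while on study. That is a fair reading, but the 1-month sentence makes it debatable.

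Fourth, the criterion defers to local regulations. As written, that phrase concerns methods of birth control and does not expressly lengthen the month. The consent form was not available, so nothing is inferred from it.

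Finally, the decay is approximate. Section 6.2.6 calls the half-life dependent on concentration and time, so a single rate may overstate what remains as levels fall. The observation that one month is about one maintenance interval, over which the protocol says saturation is maintained, does not depend on the decay model.

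**Conclusion.** The point holds as a minor, cheap improvement to participant protection. The criterion does not name the drug, and one month is short for daratumumab by the protocol's own half-life. The size depends on the reading:

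- About 30-34% remains if the month runs from the last infusion after repeated dosing.
- Less remains if it runs from a later ibrutinib dose: about 6-32% in induction, 18-32% in Cycles 3-6 and 11-32% in maintenance.
- Women who continue ibrutinib to Cycle 37 are effectively unaffected.

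These figures assume simple decay, an expected rather than measured 18-day half-life, and, for the second set, that 'study drug' means either drug. They are not bounds for an individual. The documents give no age or sex distribution for the 24 planned subjects, so no count is offered; few or no women may be concerned. No endpoint, sample size or analysis is affected.

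**What to change.** In synopsis inclusion criterion 7 and Section 7.2 criterion 8, name the drugs and require female contraception until the later of 1 month after the last ibrutinib dose and 3 months after the last daratumumab dose. Three months is about 5 half-lives at 18 days. The protocol already uses that interval for men, although it does not tie it to daratumumab clearance. The sponsor's safety group should confirm the figure, and the consent form should be made to match.

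The cost is one sentence in two places and a check of the consent form. For the women concerned, the added contraception is 90 − 30 − L days: 60 days if both drugs stop at an infusion, and 32 days if ibrutinib continued for 28 days afterwards. Visits and analyses stay as they are.
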